7.7.1 Other concomitant treatment

Other medication other than that described above, which is considered necessary for the patient's safety and well being, may be given at the discretion of the Investigator and recorded in the appropriate sections of the eCRF.

7.8 Continued access to study treatment after Part B

Patients who have not discontinued AZD9291 at the end of Part B may continue to receive AZD9291 as a single agent, if in the opinion of their treating physician they are continuing to derive clinical benefit from continued treatment (continued access).

After the end of Part B, the clinical study database will be closed. No further data will be recorded during continued access after Part B other than SAEs that may be related to IP and drug dispensing/accountability, until AZD9291 is permanently discontinued. For pregnancy reporting during continued access, see Section 6.6. Investigators will continue to follow up any existing SAEs, and report all SAEs that may be related to IP to AstraZeneca Patient Safety, until 30 days after IP is permanently discontinued, in accordance with Section 6.4 (Reporting of serious adverse events). Investigators should complete paper SAE forms and fax them directly to the AstraZeneca Patient Safety data entry site for entering onto the AstraZeneca Patient Safety database.

8. STATISTICAL ANALYSES

8.1 Statistical considerations

Statistical analyses will be performed by _____ using SAS[®] Version 9.2 or higher and, where appropriate, additional validated software.

A comprehensive Statistical Analysis Plan (SAP) will be prepared by the biostatistician prior to first patient enrolled and any subsequent amendments will be documented, with final amendments completed prior to database lock.

8.2 Sample size estimate

8.2.1 Part A

The primary objective of this part of the study is to investigate the effect of rifampicin on the PK of AZD9291. In study D5160C00005, a within-patient coefficient of variation of 20% and 23% was observed for both AUC and C_{max} , respectively, in healthy normal subjects.

However, since the variability in patients is unknown, it will be assumed that the within-patient coefficient of variation for AZD9291 in both AUC and C_{max} is 34%, an approximate 50% increase from that observed in healthy normal subjects. A 33% decrease in the exposure for AZD9291 when given with rifampicin is also assumed. With 30 evaluable

patients, the experiment-wide power for the lower bound of the 90% CI of the geometric mean ratios (AZD9291 + rifampicin/AZD9291 alone) being above 50% is 90% (95% power for each parameter).

To account for withdrawal of approximately 20% of patients, approximately 38 patients will be enrolled in order to obtain 30 evaluable patients. Additional patients may be enrolled in order to obtain at least 30 evaluable patients.

8.3 Definitions of analysis sets

Analysis sets are presented in Table 8.

Table 8 Definition of analysis sets

Analysis Set	Definition
PK analysis set	Dosed patients who have at least 1 quantifiable plasma concentration collected post-dose.
Evaluable for safety	All patients who receive at least 1 dose of AZD9291

The pharmacokineticist will agree the strategy for dealing with data affected by important protocol deviations before any formal statistical analysis is performed.

Important protocol deviations include changes to the procedures that may impact the quality of the data or any circumstances that can alter the evaluation of the PK. Examples include, but may not be limited to, vomiting following oral dosing occurring within the timeframe of 2 times the median t_{max} , sample processing errors that lead to inaccurate bioanalytical results, incomplete dose administered, incomplete PK profile collected, and/or use of disallowed concomitant medication. In the case of an important protocol deviation or event, affected PK data collected will be excluded from the summaries and statistical analyses, but will still be reported in the study result listings. Important deviations will be listed and summarised in the CSR.

8.4 Outcome measures for analyses

The following outcome measures are to be assessed in relation to the study objectives:

Analysis: Part A	Outcome Measures:
PK	
Primary AZD9291	
 $C_{ss,max}$, and AUC_{tau} (alone [Day 28] and in combination with rifampicin [Day 49])

Secondary AZD9291	
 • AUC_{τ}, and $C_{ss,max}$ [Day 77]; $t_{ss,max}$, $C_{ss,min}$, and CL_{ss}/F in all periods • trough concentrations on Days 7, 14, 21, and 28 of Period 1, Days 35, 42, and 49 of Period 2, and Days 56, 63, 70, and 77 of Period 3
Secondary AZ5104 and AZ7550	
 • AUC_{τ}, $C_{ss,max}$, $t_{ss,max}$, $C_{ss,min}$, and metabolic ratios (AZ5104 to AZD9291 and AZ7550 to AZD9291) $MRAUC_{\tau}$ and $MRC_{ss,max}$ in all periods • trough concentrations on Days 7, 14, 21, and 28 of Period 1, Days 35, 42, and 49 of Period 2, and Days 56, 63, 70, and 77 of Period 3
Secondary rifampicin	
 • AUC_{τ}, $C_{ss,max}$, $t_{ss,max}$, $C_{ss,min}$, and CL_{ss}/F
Exploratory 4 β -hydroxy-cholesterol	
 • 4β-hydroxy-cholesterol at baseline and collected throughout the 77-day AZD9291 dosing period

Safety analysis : Part A and B	Outcome Measures :
	
 • AEs/SAEs graded by CTCAE v4 • Vital signs (blood pressure/pulse/temperature/height/weight) • Laboratory parameters (clinical chemistry, haematology, urinalysis) • Physical examination • Standard 12-lead ECGs • Echocardiogram/MUGA

Pharmacokinetic analysis of the plasma concentration data for AZD9291, AZ5104, AZ7550, and rifampicin will be performed at . The actual sampling times will be used in the final PK parameter calculations.

Pharmacokinetic parameters will be derived using non-compartmental methods with Phoenix[®] WinNonlin[®] Version 6.3, or higher, (Pharsight Corp., St Louis, Missouri) and/or SAS[®] Version 9.2, or higher (SAS Institute, Inc., Cary, North Carolina).

Where possible, the following PK parameters will be determined for AZD9291 and its metabolites (AZ5104 and AZ7550) on Day 29, Day 49, and Day 77:

- AUC_{τ} : Area under the plasma concentration-time curve during a dosing interval
- $C_{ss,max}$: Observed maximum concentration at steady state, taken directly from the individual concentration-time curve

- $t_{ss,max}$: Time to reach observed maximum concentration, taken directly from the individual concentration-time curve
- $C_{ss,min}$: Observed minimum concentration over the dosing interval, tau, taken directly from the individual concentration-time curve
- CL_{ss}/F : Apparent clearance estimated as dose divided by AUC_{tau} (AZD9291 only)
- $MRAUC_{tau}$: Ratio of metabolite (AZ5104 and AZ7550) AUC_{tau} to parent AUC_{tau} adjusted for differences in molecular weight (AZD9291 = 499.62; AZ5104 and AZ7550 = 485.59)
- $MRC_{ss,max}$: Ratio of metabolite (AZ5104 and AZ7550) $C_{ss,max}$ to parent $C_{ss,max}$ adjusted for differences in molecular weight (AZD9291 = 499.62; AZ5104 and AZ7550 = 485.59)

Where possible, the following PK parameters will be determined for rifampicin on Day 49:

- AUC_{tau} : Area under the plasma concentration-time curve during a dosing interval
- $C_{ss,max}$: Observed maximum concentration after multiple dosing, taken directly from the individual concentration-time curve
- $t_{ss,max}$: Time to reach observed maximum concentration, taken directly from the individual concentration-time curve
- $C_{ss,min}$: Observed minimum concentration over the dosing interval, tau, taken directly from the individual concentration-time curve
- CL_{ss}/F : Apparent clearance estimated as dose divided by AUC_{tau} .

8.5 Methods for statistical analyses

The sample bioanalysis will be performed by [redacted]. The merging of PK concentration data with actual PK sampling times will be performed by [redacted]. The PK analysis will be the responsibility of the pharmacokineticist at [redacted]. The PK summaries, figures, and data listings as well as the statistical analysis of the PK variables will be the responsibility of the [redacted] biostatistician.

All concentration data received will be presented in data listings. Pharmacokinetic summaries will be presented for patients in the PK analysis set, as defined in Section 8.3. Data from patients excluded from the PK analysis set will be included in the data listings, but not in the summaries. Extra measurements (such as unscheduled or repeat assessments) will also not be included in summary tables, but will be included in patient listings.

For qualitative variables, the population size (N for sample size and n for available data) and the percentage (of available data) for each class of the variable will be presented. Quantitative

variables will be summarised using descriptive statistics, including n, arithmetic mean, standard deviation (SD), coefficient of variation (%CV), median, minimum, and maximum values. Additionally, geometric means and geometric %CV will be reported for PK variables (concentrations and all PK parameters, except for t_{max}).

8.5.1 Part A

For AZD9291 and its metabolites, natural log-transformed AUC_{tau} and $C_{ss,max}$, will be compared between periods using a mixed effects ANOVA with period as a fixed effect and patient as a random effect. Estimates of the mean difference between periods (Period 2 – Period 1, and Period 3 – Period 1) and corresponding 90% CIs will be calculated. The mean differences and the CIs will be back-transformed to the original scale in order to give estimates of the ratios (Period 2 versus Period 1, and Period 3 versus Period 1) and the associated 90% CIs. Additionally, back-transformed geometric means together with 95% CIs for AUC_{tau} and $C_{ss,max}$ will be estimated and presented. No effect on the PK of AZD9291 after co-administration of rifampicin will be concluded if the lower bound of the 90% CIs for the ratios (Period 2 versus Period 1) of AZD9291 AUC_{tau} and $C_{ss,max}$ are both above 50%.

For AZD9291 and its metabolites, analyses of $t_{ss,max}$ will be performed using the Wilcoxon Signed Rank Test. The Hodges-Lehman median estimator of the difference in periods (Period 2 – Period 1, and Period 3 – Period 1) and 90% CIs will be presented.

In addition to a graphical assessment of the steady state for AZD9291, a statistical evaluation of the steady state will also be made using the trough plasma concentrations collected on Days 7, 14, 21, and 28 (pre-dose and 24 hour). All valid concentrations on the natural-log scale will be analysed using ANOVA model with day as a fixed repeated effect and subject as a random effect. From this model, orthogonal contrasts with 90% CI will be formed between the mean concentration at each day and the mean concentrations for all the following days using Helmert contrasts. Precisely, Day 7 will be compared to Days 14 through 28 (24 hr) combined; Day 14 will be compared to Days 21 through 28 (24 hr) combined; and so on.

As exploratory analyses, the onset of potential induction by rifampicin (AZD9291, AZ5104, and AZ7550 troughs and concentration of 4 β -hydroxy-cholesterol after addition relative to before addition of rifampicin) will be explored. Also, the offset of potential induction by rifampicin (AZD9291, AZ5104 and AZ7550 troughs and concentration of 4 β -hydroxy-cholesterol after discontinuation of rifampicin relative to before addition of rifampicin) will be explored.

Additionally, an evaluation of potential increase in CYP3A4 enzyme activity, interpreted as the concentration of 4 β -hydroxy-cholesterol after relative to before dosing with AZD9291, will be explored. Specifically, results for 4 β -hydroxy-cholesterol, along with the ratio of post-baseline to baseline concentration, will be listed for individual patients and summarised by day and treatment. Descriptive statistics (n, arithmetic mean, SD, CV, minimum, median, maximum and geometric mean) will include the ratio of post-baseline to baseline concentration with 90% CIs calculated by natural log-transformed data. These results will be back-transformed for presentation.

Steady state of rifampicin will be assessed graphically.

A SAP will be generated to describe these analyses in more detail.

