Investigational product: AZD9291 80 mg once daily, administered orally as a tablet formulation.

Additional study drug: rifampicin 600 mg once daily, administered orally as a capsule formulation.

In Part A: all treatments (AZD9291 and rifampicin) will be administered fasted from at least 2 hours before dosing to at least 2 hours after dosing. Water is allowed as desired except for 1 hour before and after AZD9291 administration on Days 28, 49, and 77. There are no restrictions for water intake on any other study days.

In Part B and continued access: AZD9291 can be administered with or without food.

Statistical methods

Plasma concentrations of AZD9291, AZ5104, AZ7550, and rifampicin, and the derived PK parameters will be summarised by treatment using descriptive statistics and displayed graphically as appropriate.

For AZD9291 and its metabolites, natural log-transformed AUC_{τ} and $C_{ss,max}$, will be compared between periods using a mixed effects ANOVA with period as a fixed effect and patient as a random effect. Estimates of the mean difference between periods (Period 2

[rifampicin plus AZD9291] versus Period 1 [AZD9291 only, pre-rifampicin], and Period 3 [AZD9291 only, post-rifampicin] versus Period 1) and corresponding 90% CIs will be calculated. The mean differences and the CIs will be back-transformed to the original scale in order to give estimates of the ratios (Period 2 versus Period 1, and Period 3 versus Period 1) and the associated 90% CIs. Additionally, back-transformed geometric means together with 95% CIs for AUC_{τ} and $C_{ss,max}$ will be estimated and presented. No effect on the PK of AZD9291 after co-administration of rifampicin will be concluded if the lower bound of the 90% CIs for the ratios (Period 2 versus Period 1) of AZD9291 AUC_{τ} and $C_{ss,max}$ are both above 50%.

For AZD9291 and its metabolites, analyses of $t_{ss,max}$ will be performed using the Wilcoxon Signed Rank Test. The Hodges-Lehman median estimator of the difference in periods (Period 2 – Period 1, and Period 3 – Period 1) and 90% CIs will be presented.

In addition to a graphical assessment of the steady state for AZD9291, a statistical evaluation of the steady state will also be made using the trough plasma concentrations collected on Days 7, 14, 21, and 28 (pre-dose and 24 hour). All valid concentrations on the natural-log scale will be analysed using analysis of variance.

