7.2.2 Part B and continued access

In Part B and during continued access, patients may receive 80 mg oral AZD9291 once daily, given as the tablet formulation, for the duration of their participation. Based on results from Part A of study D5160C00009, AZD9291 exposure is not affected by a high fat, high calorie meal (AUC and C_{max} changes were within the no effect limit of 70-143%); therefore, in Part B and in continued access, AZD9291 can be taken with or without food.

The study treatments should be swallowed whole with approximately 240 mL of water, and not chewed, crushed, dissolved or divided.

Doses of AZD9291 should be taken approximately 24 hours apart at the same timepoint each day. Doses should not be missed. If a patient misses taking a scheduled dose, within a window of 12 hours, it is acceptable to take the dose. If it is more than 12 hours after the dose time, the missed dose should not be taken, and patients should be instructed to take the next dose at the next scheduled time. If a patient vomits after taking their AZD9291, they should not make up for this dose, but should take the next scheduled dose. Any change from dosing schedule, dose interruptions, dose reductions should be recorded in the eCRF during Part B, or per local site practice after the end of Part B (continued access).

Restrictions related to fasted administration of AZD9291 may be modified upon PK data emerging from the clinical programme.

At each dispensing visit, sufficient AZD9291 for each study period, plus overage, will be dispensed. Individual bottles will be dispensed in accordance with local practice.

The initial dose of AZD9291 can be reduced under circumstances described in Section 6.7.

AZD9291 tablets will be packed in HDPE bottles with child-resistant closures. Bottles will be dispensed to patients in the AstraZeneca packing provided. The packaging includes bottles, caps and a label. Bottle tampers should not be broken prior to dispensing study drug to a patient.

Additional information about the IP may be found in the IB.

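### The primary rule concludes 'no effect' from a criterion that only excludes a fall in AZD9291 exposure of 50% or more, and the trial is powered to reach that conclusion when the true fall is 33%

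*Protocol*

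**What the plan says.** Section 8.5.1 compares log-transformed AUCtau and Css,max between periods in a mixed-effects ANOVA and reports back-transformed ratios with 90% CIs. For the primary comparison, Period 2 (with rifampicin) versus Period 1 (AZD9291 alone), it then states a conclusion in advance: "No effect on the PK of AZD9291 after co-administration of rifampicin will be concluded if the lower bound of the 90% CIs" for the two ratios "are both above 50" per cent. The synopsis carries the same rule. There is no upper limit, no condition on whether the CI contains 100%, and no qualifier such as clinical relevance.

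Section 8.2.1 sizes the trial for that criterion. "A 33% decrease in the exposure for AZD9291 when given with rifampicin is also assumed". The within-patient CV for AUC and Cmax "is 34%, an approximate 50% increase from that observed in healthy normal subjects". With 30 evaluable patients, "the experiment-wide power for the lower bound of the 90% CI of the geometric mean ratios" "being above 50% is 90% (95% power for each parameter").

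Section 7.2.2, explaining why food restrictions are lifted in Part B, says of another AZD9291 study that AUC and Cmax "changes were within the no effect limit of 70-143" per cent.

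**The concern.** A lower confidence bound above 50% supports one statement: the geometric mean exposure has not fallen by half or more. The protocol draws a different and larger one, that the PK is unaffected. The two sections together make the gap plain. The sample size presumes a real effect of one third, and the trial is then given 90% power to declare that there is none.

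At stake is the pre-specified answer to the primary objective (Section 2.1). Section 1.3 says the data will support submissions. A study report that follows the rule as written could state no effect beside a 90% CI that shows a substantial decrease.

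**Working it through.** **Inputs.** All are from Section 8.2.1, with the rule from 8.5.1: n = 30 evaluable; within-patient CV 34%; true ratio 0.67; limit 0.50; lower bound of a 90% CI, that is one-sided 5% per parameter; both parameters must pass.

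**Precision.**
- Log-scale SD = sqrt(ln(1 + 0.34²)) = 0.3307.
- SE of the paired log difference = 0.3307 × sqrt(2/30) = 0.0854.
- t(0.95, 29 df) = 1.699, so the CI half-width factor is exp(1.699 × 0.0854) = 1.156.

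**The plan's own figure.** Noncentrality = ln(0.67/0.50)/0.0854 = 3.43. Noncentral t with 29 df gives 95.5% per parameter; 0.955² = 91.3% jointly if the two parameters are independent. At a ratio of exactly 2/3 the figures are 95.0% and 90.2%. The stated 95% and 90% reproduce. With 58 df, as three periods would allow, they are 95.9% and 92.0%, so the choice matters little.

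**What the trial would show at a true ratio of 0.67.**
- Expected 90% CI: 0.67/1.156 to 0.67 × 1.156, about 0.58 to 0.77.
- Probability that the CI lies wholly below 100%: 99.8% per parameter.
- Probability that it lies wholly below 100% and also passes the rule: 95.4% per parameter (simulation).

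**How large an observed fall can pass.** The smallest passing observed ratio at planned precision is 0.50 × 1.156 = 0.578, an observed fall of about 42%.

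**Chance of meeting the rule, by true ratio.** The joint column runs from independence (the square of the per-parameter figure) to perfect correlation.

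| True ratio | Per parameter | Both parameters |
|---|---|---|
| 0.50 | 5% | 0.25% to 5% |
| 0.55 | 29% | 8% to 29% |
| 0.60 | 67% | 45% to 67% |
| 0.67 | 95.5% | 91.3% to 95.5% |
| 0.70 | 98.6% | 97.2% to 98.6% |

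**Against the other limit that the protocol names.** For illustration only, at a true ratio of 0.67 the 90% CI falls inside 70-143% in about 1.5% of trials per parameter. At a true ratio of 1.00 it does so in 98.5% with the same 30 patients.

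**The case against.** The strongest reply is that nothing is hidden. Section 8.5.1 requires the ratio, its 90% CI and the geometric means to be presented whatever the label says, and the primary objective is to investigate the effect, not to prove its absence. That is true and limits the damage: the fault is in the conclusion attached to the estimate. It does not remove the fault, because both the rule and its power statement are fixed in this protocol.

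Four stronger readings are tempting, and the documents do not support them.

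- *Co-medication advice would go wrong.* A reader might infer that the label would feed guidance on strong CYP3A4 inducers. Appendix H already states that AZD9291 concentrations fall with rifampicin and bars potent inducers, and Section 7.7 restricts them in Part B. The protocol's guidance points the other way from the feared error.
- *The 70-143% limit is the right one and must be imposed.* Section 7.2.2 cites it for a high-fat-meal comparison in a different study. The protocol does not say that it governs induction at steady state, and its basis is not given. It shows that the same term carries two meanings; it does not settle the limit here.
- *A CI that excludes 100% is itself proof of a defect.* Any conclusion based on a limit can coexist with such a CI; under 70-143% an interval of 0.75 to 0.95 would do the same. The defect is an unqualified label resting on an unexplained limit.
- *A halving of exposure would commonly pass.* It would not: a true ratio of 0.50 passes at most 5% of the time.

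**Conclusion.** The point stands, confined to the label and the missing reason for 50%. The criterion excludes a decrease of 50% or more and nothing beyond that. On the protocol's own assumptions (true ratio 0.67, CV 34%, 30 evaluable patients), a 90% CI of about 0.58 to 0.77 is the expected result, and the rule would call it no effect with joint probability of 91.3% to 95.5%, depending on the correlation between the two parameters. These probabilities hold near the planning ratio; at a true ratio of 0.60 the joint chance drops to between 45% and 67%, and the CV in patients is itself an assumption. The logical gap between criterion and conclusion does not depend on any of these figures.

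The power calculation and the sample size are sound. A reader might infer from the mismatch that the trial is wrongly sized; it is correctly sized for the criterion, which is then misnamed.

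**What to change.** - In Section 8.5.1 and the synopsis, replace the no-effect conclusion with a statement that a decrease of 50% or more in AZD9291 exposure will be excluded if both lower 90% bounds exceed 50%.
- In Section 8.2.1, describe the 90% (95% per parameter) as power to exclude such a decrease.
- State that the size of the rifampicin effect will be interpreted from the ratios and their 90% CIs.
- If a no-effect conclusion is kept, justify its limit and reconcile it with the 70-143% cited in Section 7.2.2. Defending 50% on stated grounds and wording the conclusion to match those grounds would also be acceptable.

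The cost is wording in three places and a less favourable claim. Sample size, data collection and analysis model do not change.

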8.5.2 Population analysis of pharmacokinetic variables

The relationship between PK and treatment period and other variables may be assessed, as deemed appropriate. Results will be reported separately from the CSR.

The PK, demographic, treatment, safety and tumour response data collected in this study may also be combined with similar data from other studies and explored using population PK and/or PK methods if deemed appropriate. The results of any such analyses will be reported separately from the CSR.

